Women who are presently patients of the Neurogenetics Center of the Kennedy Krieger will be informed of the study at their routine visits. This center cares for over 100 individuals who are symptomatic carriers for this condition and it is not expected that recruitment will be an issue. However, we will also post announcements on the Kennedy Krieger Neurogenetics and the United Leukodystrophy Foundation (ULF) websites.

Women who contact us will undergo a phone screening to determine eligibility. During the telephone screening they will be asked, "Are you or do you think you might be pregnant?" If they are pregnant they are not eligible for the study. They will also be asked if there are any reasons that would prevent them from participating in an exercise program. If yes, they will be determined ineligible to participate. If they are eligible we will schedule them for their initial testing session. If they are not interested in participating or found to be ineligible we will destroy any information we have collected from them.

For healthy control subjects.

We will use posted advertisements posted in the Kennedy Krieger and in the planned fitness facilities(i.e., Curves). We will also post an announcement on the webpages of the Kennedy Krieger and ULF. Interested subjects will be told to contact the research coordinator for a telephone screening. If they are found to be eligible we will schedule them for their initial testing session. If they are found to be ineligible we will destroy any information we have collected from them.

Women will be screened during a phone interview using a standardized script. Information on the woman will be collected at that time, but if found to be ineligible or she chooses not to participate this information will be destroyed.

Women who are eligible will be scheduled for a baseline assessment. Baseline assessment will consist of a standardized sensorimotor examination including a gait assessment, MRI of the brain and cervical spinal cord, and exercise instruction. Screening medical information will be reviewed at the visit, including a question about whether the subject might be pregnant. If there are questions or concerns about eligibility or the institution of an exercise program, the PI or physician examiner will make a determination of participation.

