We will examine subjects at the level of functional disability (i.e. clinical rating scales), at the level of impairment (i.e., strength and sensation), and at the level of anatomy (i.e., MTI and DTI). The general paradigm includes four parts, requiring 1.5-3.5 hours for testing, depending on the number of activities done. Part 1 is the clinical neurological evaluation which includes clinical rating scales along with measures of lower extremity impairments and quality of life, requiring one hour. Part 2 is the laboratory testing of global walking requiring 30 minutes. Part 3 is evaluation and instruction for a custom exercise program, requiring one hour. Part 4 involves conventional imaging and measures of DTI and MTI in the brain and spinal cord to be completed in the F.M. Kirby Center in KKI, across the hall from the Motion Analysis

Date: July 1, 2013
Principal Investigator: [name]
Application Number: NA_00045673

Laboratory (requiring one hour). We will allow rest breaks as needed by each individual. Parts 1, 2, and 3 will be conducted at the Motion Analysis Laboratory located in KKI. All subjects will participate in 3 testing visits, one at baseline, one at 12 weeks and one at 18 weeks from the baseline visit. All subjects will be asked to participate in parts 1-4 at the baseline visit, and only parts 1 and 2 during visits 2 and 3.

Thus, for testing the breakdown for the time is as follows:

Baseline visit: 1 hr. clinical exam, 30 min. gait test, 1 hr. exercise instruction, 1 hr. MRI scan

12th week visit: 1 hr. clinical exam, 30 min. gait test

18th week visit: 1 hr. clinical exam, 30 min. gait test

All subjects will undergo a functional sensorimotor assessment at every testing session with the purpose of systematically documenting clinical status. The primary investigator or physical therapist and research coordinator will conduct this exam. The exam will include standard clinical measures of sensation (vibration, proprioception), strength, tone (Modified Ashworth), and passive range of motion. In addition, we will use standardized quantitative scales to evaluate walking, ataxia, and overall disease impairment in these individuals. Lastly, self report measures of quality of life and pain will be used.

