Healthy controls have the same exclusion criteria as women with AMN with 2 exceptions, (1) they can be age 21-70 years, and (2) they will not be carriers for X-ALD. They must have normal neurological function.

6. Drugs/ Substances/ Devices

- a. The rationale for choosing the drug and dose or for choosing the device to be used.

N/A

- b. Justification and safety information if FDA approved drugs will be administered for non-FDA approved indications or if doses or routes of administration or participant populations are changed.

N/A

- c. Justification and safety information if non-FDA approved drugs without an IND will be administered.

N/A

Study Statistics

- a. Primary outcome variable.

Primary outcome variables for sensorimotor impairments include: vibration sensation, strength (average values from the hip and ankle muscles, both flexion and extension, will be used), and spasticity from the ankle flexor/extensor muscles bilaterally.

The primary variables of interest for white matter integrity in this analysis will be fractional anisotropy (FA) and magnetization transfer ratio (MTR).

Other primary outcome variables include correlations to determine relationships between sensorimotor impairments and between white matter integrity variables in the tracts of interest. Multiple regression analysis we will also be used determine to what extent sensorimotor impairments are related to white matter integrity variables.

The primary outcome variable for the exercise intervention we will calculate a functional composite score (FS) for each person that will incorporate 4 tests that functionally challenge the lower extremity: 1) sit to stand, 2) Up and Go test, 3) 25-foot timed walk, and 4) 6-minute walk test.

- b. Secondary outcome variables.

To determine response to three months of the exercise intervention:

1. We will calculate pre- to post- trial differences between groups using an unpaired t test. Changes between pre- and post-trial within groups will also be compared with paired t tests.

Date: July 1, 2013
Principal Investigator: [name]
Application Number: NA_00045673

2. To determine change in hip flexion, FS from post- to follow up session within groups will be compared with paired t tests. [(Exercise_{followup}-Exercise_{post}) vs (Exercise_{post}-Exercise_{pre})], will be evaluated.

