 3. To evaluate possible time and group interactions during the intervention within groups we will use multivariate ANOVA's. Significant interactions will be evaluated with a mixed effects linear regression.
 4. To determine change in EDSS scores over each session we will use with Wilcoxon signed rank test.
 5. To determine whether specific changes in the primary outcome measures are predicted by the changes in tract specific demyelination and axonal loss (i.e., MTR and FA) we will determine how much each impairment changed from the pre- to post- session.
 6. We will conduct separate correlations to determine the relationship between the primary outcomes, and extent of demyelination and axonal loss pre- and post-intervention.
 7. Multiple regression analyses will also be used to determine which pattern of white matter damage (i.e., demyelination, axonal loss) best predicts hip flexion and FS.
- c. Statistical plan including sample size justification and interim data analysis.

Preliminary studies of heterozygote data from our laboratory suggest that a minimum of 12 subjects are needed to obtain adequate statistical power. Hip flexion strength data from female carriers are: 11.2 ± 4.6 kg. Using these values, differences between groups on the order of one SD will be statistically significant with a power of 0.8 given a sample size of 12 subjects. To account for attrition, we have added 25% to this total. Therefore, our initial plan is to have 15 female carriers for this project and 15 healthy controls. All power calculations assume two-tailed tests with $\alpha = 0.05$. Analysis will be done using Statistica software (StatSoft Inc., Tulsa OK) or Stata (StataCorp).

- d. Early stopping rules.

None.

7. Risks

- a. Medical risks, listing all procedures, their major and minor risks and expected frequency.

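### Secondary item 5 uses change in MTR and FA as its predictor, but each participant has one MRI, at baseline, so as naturally read it cannot be run; primary objective 2 can still be attempted

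*Combined protocol and SAP*

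**What the plan says.** Study Statistics, part b, lists seven items under the heading "To determine response to three months of the exercise intervention". Three of them link imaging to outcome:

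- **Item 5** asks whether changes in the primary outcomes are "predicted by the changes in tract specific demyelination and axonal loss (i.e., MTR and FA". The step it then describes concerns the outcome side only: "we will determine how much each impairment changed from the pre- to post- session".
- **Item 6** correlates the primary outcomes with the "extent of demyelination and axonal loss pre- and post-intervention".
- **Item 7** uses multiple regression to "determine which pattern of white matter damage (i.e., demyelination, axonal loss) best predicts hip flexion and FS". It gives no imaging time point and does not say whether hip flexion and the functional composite score (FS) are analysed as levels or as change.

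Section 4, part a, divides testing into four parts, with the DTI and MT imaging as Part 4. It states: "Baseline assessment will consist of a standardized sensorimotor examination including a gait assessment, MRI of the brain and cervical spinal cord". Subjects do all four parts at the first visit, "and only parts 1 and 2 during visits 2 and 3". The later visits are at weeks 12 and 18. Section 4, part b, gives about 1.5 hours per session, apart from one session of 3.5 hours that contains the scan and the exercise instruction.

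On numbers, the statistical plan states: "our initial plan is to have 15 female carriers for this project and 15 healthy controls".

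**The concern.** Item 5 names a predictor that the data collection does not appear to produce. If that is right, the analyst must replace the predictor or drop the item, possibly after seeing the data. A reader of item 5 would also expect the trial to report on white-matter change with training, which a single scan cannot show.

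The item matters beyond its place in the list. Items 5 to 7 are where the plan connects imaging to training response, and item 5 is the only one of the three that explicitly makes outcome change the thing predicted.

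**Working it through.** The question is whether a variable can be computed from the visit schedule, so the check is a count of scans, confirmed by the session lengths.

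**Session lengths reproduced** (itemised times from Section 4, part a; totals from Section 4, part b)

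| Visit | Clinical exam | Gait test | Exercise instruction | MRI | Sum | Stated |
|---|---|---|---|---|---|---|
| Baseline | 1 h | 0.5 h | 1 h | 1 h | 3.5 h | 3.5 h |
| Week 12 | 1 h | 0.5 h | none | none | 1.5 h | about 1.5 h |
| Week 18 | 1 h | 0.5 h | none | none | 1.5 h | about 1.5 h |

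A follow-up visit with a scan would take 1.5 + 1 = 2.5 h. No session of that length is listed, so the hours confirm that the only scan is at baseline.

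**Scans against what item 5 needs**

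- Scheduled per participant: 1 (baseline) + 0 (week 12) + 0 (week 18) = 1.
- Needed for a change score: 2.
- Participants with an MTR or FA change score: 0 of 15 carriers and 0 of 15 controls.

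Section 4, part b, also mentions possible future visits. They are optional, and no scan is attached to them, so they do not supply the second measurement.

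**Effect on each analysis**

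- *Item 5:* the outcome change can be computed from the baseline and week-12 visits. The imaging change cannot.
- *Item 6:* if the closing phrase describes the imaging, the post-intervention half cannot be run. If it describes only the outcomes, the item can be run in full.
- *Item 7:* it can be run with baseline imaging.
- *Primary objective 2 (Section 2):* it asks whether tract anatomy predicts response to training. That needs baseline imaging and the baseline-to-week-12 change in outcome, and both are scheduled.

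**Which text is more likely at fault**

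Hypothesis 2 in the abstract, primary objective 2 and the benefits section all predict response from anatomy or its integrity, and none refers to change in it. Baseline-only imaging is stated consistently in Section 4. This suggests that item 5 is loosely worded. It does not prove it, because item 6 leaves some doubt about whether a second scan was once intended.

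**Precision, for context**

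That objective 2 can be attempted is a statement about available data only. By the Fisher z approximation, the correlation detectable with 80% power at two-sided 0.05 is tanh[(1.960 + 0.842)/√(n − 3)]:

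- n = 15: tanh(2.802/3.464) = 0.67
- n = 12: tanh(2.802/3) = 0.73

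The n of 12 is what remains of the 15 carriers if the attrition allowance is used up (12 × 1.25 = 15).

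**The case against.** The strongest reply is that *changes* in item 5 means abnormalities present at baseline. Primary objective 1 describes the same measures as pathological abnormalities, and the only calculation item 5 spells out is the change in impairment, which needs no second scan. On that reading nothing is missing.

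The reading is possible but strained. The same word, earlier in the same sentence, plainly means change over time in the outcomes, and the sentence ends with a before-and-after comparison. Where the protocol means baseline state, it uses other terms: anatomy in objective 2 and pattern of damage in item 7. If the looser sense was intended, the plan still has to say so, and the rewording is the same.

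A second reply is that little turns on this: one secondary item is affected and the repair is textual. That stands, and it limits the severity.

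Two stronger readings are tempting, and the documents support neither:

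- A reader might infer that primary objective 2 cannot be answered or that the whole imaging-response analysis fails. The objective rests on anatomy, the baseline scan supplies it, and item 7 can be run.
- A reader might infer that a post-training scan was planned and left out of the schedule by mistake. No section schedules or describes one, and the stated aims do not need it.

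**Conclusion.** The conflict is real and confined to a secondary analysis. On its natural reading, item 5 requires a predictor that 0 of 15 carriers and 0 of 15 controls will have. Item 6 loses either nothing or its post-intervention half, depending on what its last phrase describes. Item 7 loses nothing. Primary objective 2 can be attempted on the planned data, with the limited precision shown above.

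This rests on two assumptions: that *changes* in item 5 means change over time, and that the schedule in Section 4 is what will be carried out. The balance of the text favours item 5 as the drafting slip, without settling it. Severity is minor to moderate.

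**What to change.** Reconcile Study Statistics, part b, with the schedule in Section 4, parts a and b.

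**With the schedule as planned:**

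1. Reword item 5 to test whether baseline tract-specific MTR and FA predict the baseline-to-week-12 change in the sensorimotor impairment outcomes (vibration sensation, strength, spasticity).
2. State in item 6 that the imaging is baseline and that only the outcomes are measured before and after training.
3. Keep the prediction of hip flexion and FS response in item 7, and state that both are analysed as change. FS is then not analysed twice. Hip flexion also enters the strength average in item 5, so the plan should acknowledge that overlap.
4. Draw no conclusion about white-matter change with training.

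This costs wording only, with no new visits, scans or data. The downside is that the stated imaging-change analysis is given up.

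**Only if a post-intervention scan was in fact intended:** correct the schedule and leave item 5 as a change-on-change analysis. That would serve item 5, not objective 2. It needs 15 × 1 = 15 extra scans for carriers only, or 30 × 1 = 30 for all subjects, and the week-12 visit of those scanned grows from 1.5 h to 2.5 h. The costs section names a grant for carriers' scan fees but does not mention repeat scans, so funding would need to be confirmed.

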Date: July 1, 2013
Principal Investigator: [name]
Application Number: NA_00045673

Johns Hopkins Medicine - eForm A

1. Abstract

- a. Provide no more than a one page research abstract briefly stating the problem, the research hypothesis, and the importance of the research.

X-linked adrenoleukodystrophy (X-ALD), a progressive neurodegenerative disease, is caused by a defect in the ABCD1 gene. The disease has multiple phenotypes, but the most common adult form is adrenomyeloneuropathy (AMN), which presents as a slowly progressing spastic paraparesis with sensory and autonomic dysfunction. In a previous study we linked corticospinal tract (CST) and Dorsal Column (DC) abnormalities to lower extremity sensory loss and weakness in men with AMN; however, there have been no studies evaluating these relationships in woman heterozygote carriers (i.e., women with AMN). It is unknown, in women with AMN, how the pattern of damage in the brain and spinal cord relates to disability and if these patterns predict responsiveness to treatment. While conventional magnetic resonance imaging (MRI) techniques have been used to evaluate progression of X-ALD disease burden, attempts at correlating clinical disability with axonal injury have had limited success due to clinical rating scales that do not adequately measure all aspects of the disease, coupled with an inability for routine imaging techniques to quantify relevant fiber tracts in the brain and spinal cord. We propose to comprehensively evaluate the CST and DC across the brain and cervical spinal cord with the purpose of understanding mechanisms of disability in women with AMN. We hypothesize that: 1) tract-specific magnetization transfer imaging (MTI) and diffusion tensor imaging (DTI) will predict specific sensory and motor impairments (i.e., sensory loss and weakness) and disability; and 2) tract-specific MTI and DTI will predict who is likely to respond best to progressive resistive training (PRT). For this project we are using a rigorous biologic approach that combines clinical evaluation, neuroimaging, and measures of impairment and disability to provide a more precise prognosis in terms of physical disability and to predict who is likely to respond to a physical intervention. We predict that many of the women will improve their strength and function following the PRT program. Specifically, we predict that axonal loss will be associated with irreversible disability. By contrast, demyelination may have potentially reversible injuries that would benefit from PRT in improving disability. The linking of this information will not only be important for better defining disability in women heterozygote carriers of AMN but it will also help to guide physicians and rehabilitation therapists in predicting who is likely to respond to rehabilitative interventions, as well as for optimizing outcomes for future neuroprotective pharmacological interventions.

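### Item 7 asks whether demyelination or axonal loss predicts better, but the plan has no test or interval for the difference between the two measures

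*Combined protocol and SAP*

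**What the plan says.** Section 1 (Abstract) hypothesises that "tract-specific magnetization transfer imaging (MTI) and diffusion tensor imaging (DTI) will predict specific sensory and motor impairments". It then sets the two kinds of damage against each other: "axonal loss will be associated with irreversible disability. By contrast, demyelination may have potentially reversible injuries".

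Study Statistics, a, names FA and MTR as the imaging variables of interest. It adds: "Other primary outcome variables include correlations to determine relationships between sensorimotor impairments and between white matter integrity variables in the tracts of interest". A multiple regression of impairments on the imaging variables is also planned there.

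Study Statistics, b, item 6 reads: "We will conduct separate correlations to determine the relationship between the primary outcomes, and extent of demyelination and axonal loss pre- and post-intervention". Item 7 plans multiple regression to determine "which pattern of white matter damage (i.e., demyelination, axonal loss) best predicts hip flexion and FS".

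Study Statistics, c, gives power only for "differences between groups on the order of one SD", which it calls "statistically significant with a power of 0.8 given a sample size of 12 subjects". Nothing there concerns a correlation or a difference between correlations.

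**The concern.** Item 7 asks a comparative question, and the abstract frames axonal loss and demyelination as a contrast. The analyses named to answer it are correlations tested one at a time and a regression with no stated rule for choosing the better predictor. No section gives a test between correlations measured in the same women, a contrast of regression coefficients, or a model-comparison criterion.

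If one correlation is significant and another is not, that does not show that they differ. In a sample this small, two equally strong relationships will often fall on opposite sides of the significance threshold by chance. The same can happen to two coefficients in a joint regression. What is at stake is the statement the study hopes to make about which kind of damage predicts function and response to training. The issue does not depend on how many tests are run, since it arises with only two.

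**Working it through.** **The plan's own figure.** The attrition step reproduces: 12 × 1.25 = 15 carriers. The 12 itself does not reproduce under the stated inputs (1 SD, two-tailed 0.05, power 0.8): 2 × (1.96 + 0.84)² / 1² = 15.7, so 16 per group by the normal formula. That is a separate matter. For this point it matters only that the figure concerns a difference in means, and that 12 to 15 carriers are available.

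**Inputs.** From the documents: n = 12 or 15 and two-tailed alpha 0.05 ("All power calculations assume two-tailed tests"; applying the same level to the correlations is an assumption). The documents give no correlations, so all values of r below are assumptions.

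**Threshold for one correlation.** r_crit = t / √(n − 2 + t²), with t the 97.5% point on n − 2 df.
- n = 15: 2.160 / √(13 + 4.667) = 0.514.
- n = 12: 2.228 / √(10 + 4.965) = 0.576.

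True correlations near 0.5 or 0.6 sit close to these thresholds, so each test behaves much like a coin toss.

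**Two equal relationships.** Trivariate normal data were simulated (one outcome, two imaging measures, 100,000 data sets per cell), with both imaging measures having the same true r with the outcome. The table gives the percentage of trials in which exactly one of the two is significant.

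| n | True r (both) | Inter-measure r | Separate correlations | Joint regression coefficients |
|---|---|---|---|---|
| 12 | 0.4 | 0.5 / 0.7 | 29 / 23 | 20 / 14 |
| 12 | 0.5 | 0.5 / 0.7 | 36 / 28 | 29 / 20 |
| 12 | 0.6 | 0.5 / 0.7 | 38 / 30 | 42 / 28 |
| 15 | 0.4 | 0.5 / 0.7 | 32 / 25 | 25 / 17 |
| 15 | 0.5 | 0.5 / 0.7 | 37 / 29 | 37 / 24 |
| 15 | 0.6 | 0.5 / 0.7 | 33 / 26 | 51 / 36 |

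The ranges are therefore 23–38% for correlations and 14–51% for coefficients. The Williams test of the difference rejects in about 5% of trials in every cell. At n = 15 and r = 0.5, it finds a difference in only 10–12% of the trials that split.

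**Outside that range.** At n = 15, with inter-measure r from 0.7 down to 0.3, correlations split in 7–9% of trials at true r = 0, 19–28% at 0.3 and 15–21% at 0.7. The rate peaks where each test has middling power.

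**A worked contrast.** Suppose the observed r are 0.6 and 0.2, with inter-measure r 0.5. The Williams statistic is

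t = (r₁ − r₂) √{ (n − 1)(1 + r₁₂) / [ 2|R|(n − 1)/(n − 3) + r̄²(1 − r₁₂)³ ] }, on n − 3 df,

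where |R| = 1 − 0.36 − 0.04 − 0.25 + 2(0.6)(0.2)(0.5) = 0.47 and r̄ = 0.4, so the last term is 0.16 × 0.125 = 0.02.
- n = 15: 0.4 × √(21 / 1.117) = 1.73, p = 0.11.
- n = 12: 0.4 × √(16.5 / 1.169) = 1.50, p = 0.17.

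At either n, 0.6 passes its threshold and 0.2 does not, yet the difference is not established.

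**Power of the direct test.** For true r 0.6 versus 0.2 (inter-measure r 0.5), power is about 38% at n = 15 and 30% at n = 12. For 0.6 versus 0.3, it is 18–37% at n = 15, and about 40 to 85 women would be needed for 80% (inter-measure r 0.7 to 0.3).

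**The case against.** - **Regression is planned too.** A reader might infer that the hypotheses rest on separate correlations alone. They do not: multiple regression appears in both parts a and b, and item 7 aims it at demyelination versus axonal loss. If MTR and FA enter together, that model could carry the comparison. This stands. What is missing is the contrast or criterion, and without one the joint model splits about as erratically as the correlations.
- **The plan does not commit the error.** A reader might infer that specificity will be read from significant versus non-significant results. No section says so. It is a risk left open.
- **The tract contrast is only implied.** In the abstract, tract-specific describes how the imaging is measured, and the first objective asks about extent of association. No section predicts that the corticospinal tract (CST) relates more strongly than the dorsal column (DC) to strength, or the reverse for vibration. The point therefore applies to tracts only if such a difference is to be claimed.
- **A split is not a false conclusion.** The percentages are the chance of discordant significance under assumed correlations. They become an error rate only if a ranking is drawn from the split.
- **The direct test has low power.** With a true 0.6 versus 0.2 at n = 15, it would miss the difference in about 62% of studies. This is a good reason to call the contrasts exploratory and report intervals. It does not make an untested ranking more reliable.

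**Conclusion.** The point holds in a limited form. The plan poses a comparative question about demyelination and axonal loss and supplies no test, interval or criterion to answer it. With 12 to 15 carriers, a ranking based on which measure reaches significance would be unreliable: for equally strong relationships, discordance is about 23–38% for correlations and 14–51% for joint coefficients. These sizes rest on normal data and on assumed true r of 0.4 to 0.6 with inter-measure r of 0.5 to 0.7. Other values change the percentages but not the absence of a comparative analysis.

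The wording of item 6 might also suggest comparing correlations before and after training. The documents do not support including that contrast. Section 4.a schedules MRI at baseline only, while items 5 and 6 refer to changes in MTR and FA and to damage both pre- and post-intervention. Those sections must be reconciled first.

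**What to change.** In Study Statistics, b, add the following.

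- For MTR versus FA, with hip flexion and with FS, pre-specify the difference between the two dependent correlations (Williams/Steiger, or a bootstrap over women) or between standardised coefficients in the joint model. Report it with a 95% confidence interval.
- Do the same for CST versus DC if a tract difference is to be claimed.
- Sign the measures in the same direction before comparing them.
- Label these contrasts exploratory, and report each association with its own confidence interval.
- Do not state that one metric or tract predicts better than another unless the interval for the difference excludes zero.

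This uses the baseline imaging and outcomes already planned and costs only a little analysis text. The real price is fewer claims of specificity, given the low power shown above.
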